2.3.1 Patient disposition

The number of subjects screened will be presented. In addition, the reasons for screen failures will be provided. The number and percentage of subjects in the randomized set who completed study periods and who discontinued the study prematurely (including the reason for discontinuation) will be presented for each treatment group and all subjects.

For each protocol deviation, the number and percentage of subjects for whom the deviation applies will be tabulated.

2.4 Treatments (study treatment, concomitant therapies, compliance)

2.4.1 Study treatment / compliance

The analysis of study treatment data will be based on the safety set.

The number of secukinumab 2mL auto injections, 1mL secukinumab syringe, secukinumab placebo injections will be summarized by treatment group by means of contingency tables.

The duration of exposure to study treatment will be summarized by treatment group. In addition, the number of subjects with exposure of at least certain time thresholds will be displayed. The following categories will be presented: “any exposure”, “ ≥ 1 week”, “ ≥ 2 week”, “ ≥ 3 week”, “ ≥ 4 weeks”, “ ≥ 8 week”, “ ≥ 12 weeks”, “ ≥ 16 weeks”, “ ≥ 28 weeks”, “ ≥ 40 weeks” and “ ≥ 52 weeks”.

Duration of exposure will be defined as the time from first dose of study medication to the last dose plus 84 days or last visit whichever occurs earlier. i.e., for subjects who discontinued or have their last visit earlier than 84 days, the end of study treatment exposure will be the date of the last study visit or in the corresponding treatment period.

Duration of exposure (days) = min (“end of study period” date, last dose date +84) – first dose date +1

Duration of exposure (years) = duration of exposure (days) / 365.25

Duration of exposure (100 subject years) = duration of exposure (years) / 100

The analyses of duration of exposure described above will be done for the treatment period up to Week 16 for the primary analysis, with the last category “ ≥ 16 weeks”..

2.4.1.1 Visit window

Visit-windows will be used for the data that is summarized by visit; they are based on the study evaluation schedule and comprise a set of days around the nominal visit day. For any assessment, there are the protocol defined scheduled visits around which visit windows were created to cover the complete range of days within the study. The visit windows are shown in [Table 2-3](#). In this table, the days are counted since the first dose of study treatment (Day 1) for safety assessments, and the days are counted since the date of randomization for efficacy assessments. These visit windows apply to measurements taken at every visit.

When visit windows are used, all visits will be re-aligned, i.e., they will be mapped into one of the visit windows. E.g., if the *Week 4* visit of a subject is delayed and occurs on Day 60 instead of on Day 29, it will be re-aligned to visit window *Week 8*. In the case of major deviations from the visit schedule, or due to unscheduled visits, several assessments of a subject may fall in a particular visit window (either scheduled or unscheduled). Statistical approaches to handle multiple assessments in a given visit window are specified in [Section 2.4.1.2](#).

For parameters which are not collected at every visit (e.g., DLQI), visit windows will be combined. For example, if a parameter is measured at Week 12 and Week 28 only, Week 12 visit window will extend from Day 2 to Day 99 (combining Week 1 to Week 12 visit windows), and Week 28 will extend from Day 100 to Day 239.

Assessments from treatment period 2 will not be considered for treatment period 1, and treatment period 1 visits will not be mapped into treatment period 2.

Table 2-3 Assessment windows for scheduled visits

Analysis Visit	Week	Scheduled Day	Visit Window
Baseline	BSL	1	-28 days to Day 1*
Week 1	1	8	Day 2-11
Week 2	2	15	Day 12-18
Week 3	3	22	Day 19-25
Week 4	4	29	Day 26-43
Week 8	8	57	Day 44-71
Week 12	12	85	Day 72-99
Week 16	16	113	Day 100-155
Week 28	28	197	Day 156-239
Week 40	40	281	Day 240-323
Week 52	52	365	Day 324-421

* Baseline measurement before the first drug administration for safety assessments and before the randomization for efficacy assessments.

Of note: subject's height will not be remapped according to the analysis visit window.

The analysis visit will be used for listing of visit and period for safety data. If a visit falls after the last visit window (after Day 421) it is not assigned an analysis visit and will be listed under label "After Week 52".

2.4.1.2 Multiple assessments within visit windows

When there are *multiple assessments* in a particular visit window, the following rules are applied to select one value "representing" the subject in summary statistics in a visit window (See [Table 2-4](#)).

For baseline assessment definition see [Section 2.1.1.3](#). For post-baseline visit windows the following applies (unless otherwise specified):

- for *quantitative variables*, the *closest* to the actual visit is chosen (if two assessments have the same distance, then the earlier one will be chosen);
- for *qualitative variables*, the *worst* record is selected. It is noted that in the analyses performed, *worst* case is always well defined (e.g., for urine protein values "+" and "++", the worst case is defined as "++"),
- in case qualitative variables are based on quantitative variables, e.g. PASI 90 response, the visit will be assigned to the quantitative variable, and this visit will be used for the derived qualitative variable.

Table 2-4 Rules for selecting values for analysis within a given visit window

Timing of measurement	Type of data	Rule
Baseline	All data	See Section 2.1.1.3 .
Post-baseline efficacy	All data except for PRO, e.g., PASI, IGA	The measurement closest to the target day will be used. In the event two measurements are taken equally apart (e.g., 1 day before target date and 1 day after), the earlier one will be used. If two measurements are taken on the same day then select the first one using eCRF visit number. If two measurements have been taken on the same day and same visit then select the worst.
Post-baseline efficacy	PRO data	The measurement closest to the target day will be used. In the event two measurements are taken equally apart (e.g., 1 day before target date and 1 day after), the earlier one will be used. If two measurements have been taken on the same day, select the worst. If two measurements have the same value, select the first one using eCRF visit number.
Post-baseline safety	Summary visit information (e.g. laboratory values, vital signs, etc.)	The (non-missing) measurement closest to the target day will be used. In the event two measurements are taken equally apart (e.g., 1 day before target date and 1 day after), the earlier one will be used. If two measurements are taken on the same day then select the first one (using the time). If two measurements are taken on the same date/time then use the first eCRF visit number (assuming this is the planned visit). If two measurements are taken on the same date/time/eCRF visit number then take the average value of these two results.
Post-baseline safety	Notable abnormalities (e.g. vital signs) and CTCAE grades for laboratory values	The most extreme measurement in the window will be used. Note this means a subject can have a notably high and notably low measurement within an analysis period.

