The Treatment Period 1 starts with the randomization of eligible subjects followed by the first dosing. At the start of Treatment Period I, eligible subjects will be randomized at a 2:2:1:1 ratio to one of the four treatment groups ([Section 6.1.1](#)). In order to achieve a balanced weight distribution in each treatment arm, randomization in these four groups will be stratified by body weight at baseline (< 90 kg or \geq 90 kg). Subjects are then visiting the study site at Week 1, 2, 3, 4, 8 and 12, where they will receive study treatment (secukinumab 300 mg 2 mL AI, secukinumab 300 mg 2 x 1mL PFS, or placebo).

Assessments for the primary endpoints are done for all treatment arms at Week 12 prior to dosing. This time-point is the End of Treatment Period 1 (EOT1).

- Treatment Period 2 (of 40 weeks, double-blind between Week 12 dosing and Week 52)

[figure not shown]
The Treatment Period 2 is a maintenance period for the study treatment and starts with the Week 12 dosing. Doses of study treatment are then self-administered weekly up to Week 16 and every four weeks up to Week 48 for all treatment arms.

Week 52 is the planned End of Treatment Period 2/End of Study (EOT2/EOS).

Subjects who prematurely discontinue study treatment must perform EOT1 or EOT2/EOS approximately four weeks after their last dose of study treatment, depending if they are in Treatment Period 1 or 2, respectively.

Safety, efficacy [REDACTED] will be performed according to the visit schedule as described in [Table 8-1](#).

Figure 3-1 Study design

In the figure, the solid arrow means active drug dosing while the dotted arrow means placebo dosing.

4 Rationale

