6.7.2 Instruction for prescribing and taking study treatment

All doses of study treatment (secukinumab and/or placebo) will be self-administered by the subject either at the study site or at home.

The first use at Randomization and the Visit Week 1 assessments of the self-injection will take place in the context of an observed assessment under the supervision of one site staff member. Each assessment will be conducted on a 1:1 basis.

At the Randomization Visit the subjects will be instructed by the site staff walking them through the Instructions For Use (IFU) on how to self-inject via the PFS and AI (the IFU brochure containing detailed information about self-administration of study treatment should be provided to each subject at the beginning of the study). After providing detailed explanations/instructions, subjects will then be asked to raise any questions. Thereafter, they will proceed with self-injection. At Week 1 subjects will be asked to refer to the IFU and to proceed with self-injection of the actual study drug (i.e., without a detailed explanation/instruction on handling the syringe and auto-injector). At Randomization and Week 1, site staff will observe and complete the self-injection assessment checklist ([Table 8-5](#)) and the possible hazard assessment check list ([Table 8-6](#)) for the 2 mL auto-injector.

Home administrations should be done at pre-defined visits ([Table 8-1](#)) and can be performed by the subject. If self-administration is not chosen, these administrations can be performed by a trained caregiver. If the subject or caregiver is not able/confident to perform home administration, the subject will be allowed to return to the site for administration of the medication. However, during those site visits no additional assessments will be required.

During home administrations subjects are expected to contact the investigator/site staff in case they are experiencing any AE/SAEs or have any concerns.

Administration

All doses of study treatment that are administered at the study site should be performed after the study assessments for the visit, including blood sampling and the completion of DLQI questionnaire by the subjects, have been completed.

The first study treatment administration will occur at the Randomization/baseline Visit, after all study scheduled assessments have been performed (and inclusion/exclusion criteria confirmed) and only after the scheduled blood samples have been drawn.

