- if it has not been approximately 4 weeks post last dose of study treatment, then the subject should be scheduled to return 4 weeks post last dose for their EOT1 assessments or EOT2/EOS assessments.

Assessments detailed in [Table 8-1](#) should be completed and recorded in the eCRF.

If the subject cannot or is unwilling to attend any visit(s), the site staff should maintain regular telephone contact with the subject, or with a person pre-designated by the subject. This telephone contact should preferably be done according to the study visit schedule.

After study treatment discontinuation, at a minimum, in abbreviated visits, the following data should be collected at clinic visits or via telephone/email contact:

- new / concomitant treatments
- adverse events/Serious Adverse Events

The investigator must also contact the IRT when the subject completes EOT1 or EOT2/EOS visit to register the subject's discontinuation from study treatment.

If discontinuation occurs because treatment code has been broken, please refer to Emergency breaking of treatment code section.

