2.5.3 Handling of missing values/censoring/discontinuations

Response variables based on PASI score and IGA mod 2011 categories will be imputed with multiple imputation (MI) as primary imputation method for the missing values.

Multiple imputation (MI) is a simulation based approach where missing values are replaced by multiple Bayesian draws from the conditional distribution of missing data given the observed data and covariates, creating multiple completed data sets. These completed data sets can then be analyzed using standard methods. Within this analysis the PASI score or IGA mod 2011 categories will be imputed and response variables will be derived based on the imputed scores. In the multiple imputation analysis the response status will be imputed based on the individual treatment arm information.

(Modified) Non-responder imputation will be used as a sensitivity method: Missing values with respect to response variables based on PASI score and IGA 2011 categories will be imputed with non-response regardless to the reason for missing data (e.g. premature study discontinuation, missed visit, administrative issues), exceptions will apply to the following:

- If a subject dropped out of the study prior to last scheduled visit and being responder consecutively at least for two preceding visits, the subject will be imputed as responder after discontinuation and up to the last scheduled visit.
- If a subject who was responder at visit $x-1$ and visit $x+1$ but has missing data at visit x , then the subject will be imputed as responder for visit x as long as the distance between the scheduled visits $x-1$ and x is 4 weeks or less, and the distance between the scheduled visits x and $x+1$ is 4 weeks or less. Otherwise missing data will be imputed with non-response.

Some examples are illustrated below:

Visit	1	2	3	4	5	6	7	8	9	10
Pat										
A	R	NR	R		NR	NR	NR	NR	NR	NR
A imp										
B	NR	R	R		R	R	R	R	R	R
B imp										
C	R	NR	R		NR	NR	R	R	R	NR
C imp										

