Summary tables for PASI scores and IGA mod 2011 categories will be imputed using MI. The mean for PASI score and the number (%) for IGA mod 2011 categories as well as their 95% confidence intervals will be given. In addition, PASI scores and IGA mod 2011 categories based on LOCF imputation will be provided in summary tables and listings.

Note: Only PASI and IGA mod 2011 based response variables are imputed with multiple imputation or non-response, other response variables (e.g. DLQI 0 or 1 achievement) will be imputed with LOCF.

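### The closest-to-target rule drops the EOT2 PASI/IGA after a last dose at Week 16, 28 or 40, and the SAP does not say whether imputation then ignores it (minor; affects results after Week 12 only)

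*SAP*

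**What the plan says.** **Timing of EOT2.** Protocol Section 3: "Subjects who prematurely discontinue study treatment must perform EOT1 or EOT2/EOS approximately four weeks after their last dose of study treatment". Protocol 9.1.1 repeats this for subjects seen earlier than that: "then the subject should be scheduled to return 4 weeks post last dose for their EOT1 assessments or EOT2/EOS assessments". Protocol Table 8-1 lists PASI and IGA at EOT2/EOS.

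**Order at a site visit.** Protocol 6.7.2: "All doses of study treatment that are administered at the study site should be performed after the study assessments for the visit". The scheduled PASI and IGA therefore already exist when the dose of that visit is given.

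**Windows.** SAP 2.4.1.1: "When visit windows are used, all visits will be re-aligned". Table 2-3 sets Week 16 at Day 100-155, Week 28 at Day 156-239, Week 40 at Day 240-323 and Week 52 at Day 324-421.

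**Selection within a window.** SAP Table 2-4, in the row that names PASI and IGA: "The measurement closest to the target day will be used". Ties go to the earlier value. The bullets above the table, which hold unless something else is specified, instead take the worst record for qualitative variables.

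**Missing data.** SAP 2.5.3 makes multiple imputation (MI) primary and a modified non-responder imputation (NRI) the sensitivity method. Under the latter, for a subject who leaves the study after responding at two consecutive visits, "the subject will be imputed as responder after discontinuation and up to the last scheduled visit". The same section adds that "PASI scores and IGA mod 2011 categories based on LOCF imputation will be provided in summary tables and listings". SAP 2.7.3 refers to 2.5.3 for the secondary endpoints.

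**The concern.** Whether a stopping subject's final efficacy value is used depends only on which dose happened to be last. The subjects concerned have just stopped treatment, and some may have stopped because the effect was waning. If the dropped value shows non-response and no later efficacy visit follows, the analysis may fill Weeks 28 to 52 from the earlier, better value although a worse one was measured.

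At stake are the by-visit PASI and IGA results after Week 12, which are secondary endpoints, and the optional risk difference between auto-injector and pre-filled syringe up to Week 52 (SAP 2.7.1).

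**Working it through.** **1. Reproduce the windows.** Target day = 7 × week + 1. The upper end of a window is the midpoint to the next target, rounded down:
- Week 12: (85 + 113)/2 = 99
- Week 16: (113 + 197)/2 = 155
- Week 28: (197 + 281)/2 = 239
- Week 40: (281 + 365)/2 = 323

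These match Table 2-3, as do the earlier windows.

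**2. Why only three dose weeks.** The Week 16, 28 and 40 windows run 42 days past target (155 − 113, 239 − 197, 323 − 281). EOT2 comes at +28 days, so it stays inside. The Week 4, 8 and 12 windows run only 14 days past target (43 − 29, 71 − 57, 99 − 85), so a visit at +28 days leaves them.

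**3. Map EOT2 = last-dose day + 28.**

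| Last dose | EOT2 day | Window | Distance to target | Scheduled PASI/IGA already in window | EOT2 value |
|---|---|---|---|---|---|
| Week 12 (85) | 113 | Week 16 | 0 | no | used |
| Weeks 13, 14, 15 | 120, 127, 134 | Week 16 | 7, 14, 21 | no | used |
| **Week 16 (113)** | **141** | **Week 16** | **28** | **yes, distance 0** | **dropped** |
| Week 20 (141) | 169 | Week 28 | 28 | no | used |
| Week 24 (169) | 197 | Week 28 | 0 | no | used |
| **Week 28 (197)** | **225** | **Week 28** | **28** | **yes, distance 0** | **dropped** |
| Week 32 (225) | 253 | Week 40 | 28 | no | used |
| Week 36 (253) | 281 | Week 40 | 0 | no | used |
| **Week 40 (281)** | **309** | **Week 40** | **28** | **yes, distance 0** | **dropped** |
| Week 44 (309) | 337 | Week 52 | 28 | no | used |

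Visit timing hardly changes this. If the scheduled visit and its dose are *k* days early, the distances are *k* and 28 − *k*, and EOT2 wins only if 28 − *k* < *k*, that is, at 15 days early or more.

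**4. Modified NRI on windowed visits.** Take a subject who responds at every scheduled visit, is a non-responder at EOT2 and has no later efficacy visit.

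| Last dose | EOT2 ignored | EOT2 counted as most recent visit |
|---|---|---|
| Week 16 | responder at 28, 40, 52 | non-responder at 28, 40, 52 |
| Week 28 | responder at 40, 52 | non-responder at 40, 52 |
| Week 40 | responder at 52 | non-responder at 52 |

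**5. LOCF and MI.** On windowed values, LOCF carries the earlier scheduled value and MI conditions on it. To illustrate MI, with every input assumed, let PASI improvement be normal with mean 88%, SD 18 and between-visit correlation ρ. Then

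P(PASI 75 at next visit | x) = 1 − Φ((75 − [88 + ρ(x − 88)]) / (18√(1 − ρ²))).

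- Retained value x = 85: 0.77 at ρ = 0.5, 0.84 at ρ = 0.8.
- Dropped value x = 50: 0.35 at ρ = 0.5, 0.05 at ρ = 0.8.

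**6. Size.** The documents give no dropout rate. Assume a share *d* stops in Period 2, spread evenly over the 12 dose weeks before Week 48 (12-16, 20, 24, 28, 32, 36, 40, 44). Subjects affected in a 40-subject arm = 40 × *d* × 3/12:
- *d* = 5%: 0.5 subjects, 0.5/40 = 1.25 points
- *d* = 10%: 1 subject, 2.5 points
- *d* = 20%: 2 subjects, 5 points

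These are upper limits at Week 52, reached only if every affected subject had lost response and had no later visit.

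**The case against.** The strongest objection is that the SAP never says the rules of 2.5.3 run on windowed values. Windows are introduced for data summarised by visit. Read literally, the last observation for LOCF is EOT2, and a non-responder EOT2 counted as a preceding visit would block the carry-forward. This stands as an ambiguity. The windowed reading is the likelier one, because the example in 2.5.3 has ten visits and Table 2-3 has ten post-baseline analysis visits, but the text does not settle it.

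Other points that stand:
- **EOT2 is not an off-drug value.** Four weeks is the maintenance dosing interval, and the Week 28 and 40 values are also read about four weeks after the previous dose slot. A reader might infer a proven upward bias; the documents support only a plausible one.
- **Later visits may exist.** Protocol 9.1.1 asks subjects who stop treatment to return where possible, and observed later data remove the problem. The stated minimum after discontinuation, however, contains no PASI or IGA.
- **The affected tables are fewer than they seem.** SAP 2.5.3 and 5.1.5 limit imputation of PASI/IGA response to MI or non-response, so no LOCF response-rate table is planned. The only NRI analysis named (SAP 2.5.4) concerns Week 12 endpoints, and by-visit response uses MI (SAP 5.4.4).
- **The later MI input is unspecified.** The PROC MI code stops at the primary endpoint week, so one cannot say that EOT2 never enters it.
- **IGA may be protected.** The worst-record bullet would keep a worse EOT2 IGA. Table 2-4 names IGA and probably governs, but the two rules conflict.
- **Both active arms share the rule**, so part of any effect should cancel in the risk difference between devices.

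**Conclusion.** The point holds, as a minor one. On the plan's own windows and selection rule, the EOT2 PASI and IGA are dropped after a last dose at Week 16, 28 or 40 and used after a last dose at Week 20, 24, 32, 36 or 44. No rule clearly protects the dropped value.

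That an observed loss of response is then overwritten depends on two conditions: 2.5.3 is applied to windowed visits, and the subject has no later efficacy visit. Overwriting up to Week 52 also rests on the SAP wording, since Protocol 12.4.3 applies the exception to the last scheduled visit only. Under modified NRI the overwriting is then certain for a subject with two preceding responder visits; under MI the dropped value would be ignored and later response drawn at random.

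Each affected subject moves a 40-subject arm by 1/40 = 2.5 points. The range of about 1.3 to 5 points at Week 52 is a ceiling that rests on assumed dropout. A reader might infer more by spreading 10% dropout over only the eight doses from Week 16 to Week 44, which gives 40 × 0.10 × 3/8 = 1.5 subjects and 3.75 points. Nothing in the documents supports that timing.

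A reader might also infer that the main result is at risk. It is not: SAP 2.4.1.1 keeps Period 2 assessments out of Period 1, so the co-primary and key secondary endpoints are untouched. After Week 12 the SAP plans summaries and an optional risk difference, not hypothesis tests of efficacy.

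**What to change.** Add to SAP 2.4.1.2, with a reference from 2.5.3:

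*For PASI and IGA, an EOT2 assessment after treatment discontinuation that is not selected for its window still counts as the most recent visit in the two-preceding-visits rule and as the last observation for LOCF.*

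Also reconcile the worst-record bullet for qualitative variables with the Table 2-4 rule for IGA, and state which visits enter the MI after Week 12.

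EOT2 should not have to be mapped to the next analysis visit. It lies 56 days before that target (197 − 141, 281 − 225, 365 − 309), twice the 28 days the windows accept after a last dose at Week 20, 32 or 44. If its value is wanted in the MI, it can enter as an auxiliary variable.

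The cost is a small programming rule and no new data. Late response rates would usually be slightly lower. Occasionally a subject would newly qualify for the carry-forward, for example one who did not respond at Week 12 but responded at Week 16 and at EOT2.
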